Nudging High-acuity Emergency Department Patients to Schedule a Follow-up Visit
(NCT06535347)

Study Protocol with Statistical Analysis Plan

August 9, 2024

Study Protocol

Background

The goal of this campaign is to reduce unnecessary emergency department (ED) visits/encourage patients with high acuity visits who have a Geisinger primary care provider (PCP) in the Community Medicine Service Line (CMSL) assigned to follow up with an appropriate provider (their PCP or a specialist) in the future. In this campaign, patients will be assigned to receive or not receive outreach following ED discharge that is aligned with this goal. Outreach will occur via a text message, as well as information added to the patient's after visit summary (AVS), and will include a call to action for the patient to schedule a follow-up appointment with their PCP or a specialist. The SMS messages and AVS will include a phone number to call to schedule an appointment. The SMS messages will also include a hyperlink to self-schedule an appointment. The study will assess whether ED use differs across patients in different outreach conditions. It will also examine whether patients followed through on the message-specific calls to action in the messages differently across conditions.

Objectives

The study will involve randomized assignment of patients to different versions of outreach, including a treatment arm that encourages patients in non-emergent situations to call their PCP's office or a specialist. Patients will also be provided a number to call through which they can schedule an appointment with a provider. SMS messages will include a hyperlink to self-schedule an appointment with a provider. Both SMS text messages (at 1 day, or 1 day and 8 days, post-discharge) and AVS (printed or available via patient portal upon discharge) will be used for active outreach. The control arm will receive the current standard system outreach and AVS. Data will be analyzed to determine which version is most effective at reducing ED use.

Design

This study is a randomized controlled trial with three study arms. Patients will be randomized to receive or not receive SMS texts (at 1 day or 1 and 8 days post discharge) and a modified AVS upon ED discharge.

Methods

At the time of an eligible patient's discharge from the ED, that patient will be assigned to one of the following study arms, based on which of several ranges of randomized numbers that patient was originally assigned in their electronic chart:

1. **Current standard practice (control arm):** Patients in this arm will receive the current standard AVS and whatever typical system outreach occurs.
2. **Follow-up scheduling single notice (treatment arm):** Patients in this arm will receive suggestions for non-ED follow-up care with their PCP or a specialist via SMS messages at 1 day post discharge and in their AVS. The outreach will include a scheduling phone number to call. SMS messages will include a hyperlink to self-schedule with a Geisinger provider.
3. **Follow-up scheduling notice plus reminder (treatment arm):** Patients in this arm will receive suggestions for non-ED follow-up care with their PCP or a specialist via SMS messages at 1 and 8 days post discharge and in their AVS. The outreach will include a

scheduling phone number to call. SMS messages will include a hyperlink to self-schedule with a Geisinger provider.

Power Analysis

With 7,500 patients, we would have 80% power to detect a 3.0% absolute decrease in ED visits between each active arm and the control arm, with two-tailed alpha of .15, assuming a 33% baseline rate of subsequent ED visits within 120 days. The target effect size and number of patients are largely informed by practical considerations regarding the acceptable duration of the intervention (maximum of 6 months, regardless of whether the full sample is achieved), with an effect deemed useful if achieved.

Project Status

As of August 9, 2024, when this document was uploaded, no messages have been sent or data collected or analyzed.

Statistical Analysis Plan

Planned Analyses

Primary Outcome: ED visit [Time Frame: within 120 days following day of discharge]

Question: Does outreach decrease ED visits when including information about follow-up care?

Analysis (Confirmatory): We will test the hypothesis that SMS text plus AVS outreach (with or without reminder) decreases the likelihood patients will visit the ED in the 120 days following day of discharge. We will run an OLS regression including a categorical predictor variable coding for experimental arm (0 = control arm, 1 = single message arm, 2 = message plus reminder arm).

Other Pre-specified Outcomes

We will run the analysis described above on the following additional outcomes:

1. PCP/specialist appointment scheduled

PCP/specialist appointment scheduled (yes/no)

[Time Frame: within 7 days following day of discharge]

2. PCP/specialist visit attended

PCP/specialist appointment attended (yes/no)

[Time Frame: within 7 days following day of discharge]

3. PCP/specialist appointment scheduled

PCP/specialist appointment scheduled (yes/no)

[Time Frame: within 14 days following day of discharge]

4. PCP/specialist visit attended

PCP/specialist appointment attended (yes/no)

[Time Frame: within 14 days following day of discharge]

5. PCP/specialist appointment scheduled

PCP/specialist appointment scheduled (yes/no)

[Time Frame: within 30 days following day of discharge]

6. PCP/specialist visit attended

PCP/specialist appointment attended (yes/no)

[Time Frame: within 30 days following day of discharge]

7. PCP/specialist appointment scheduled

PCP/specialist appointment scheduled (yes/no)

[Time Frame: within 60 days following day of discharge]

8. PCP/specialist visit attended

PCP/specialist appointment attended (yes/no)

[Time Frame: within 60 days following day of discharge]

Analysis Notes

Recent work suggests that OLS regressions are appropriate in randomized experiments with binary outcome variables such as ours (Gomila, 2021).

Reference

Gomila, R. (2021). Logistic or linear? Estimating causal effects of experimental treatments on binary outcomes using regression analysis. *Journal of Experimental Psychology: General*, 150(4), 700-709. <https://doi.org/10.1037/xge0000920>

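### Should the primary outcome separate unnecessary ED visits from the rest, given the campaign goal?

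*Combined protocol and SAP*

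**What the plan says.** The Background begins with the campaign: "The goal of this campaign is to reduce unnecessary emergency department (ED) visits/encourage patients with high acuity visits", the second part being follow-up with a PCP or specialist. Later in that paragraph it turns to the trial: "The study will assess whether ED use differs across patients in different outreach conditions". It then adds a second aim: "It will also examine whether patients followed through on the message-specific calls to action in the messages differently across conditions".

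The Objectives close with "Data will be analyzed to determine which version is most effective at reducing ED use". The Power Analysis counts ED visits of any kind, "assuming a 33% baseline rate of subsequent ED visits within 120 days". In the SAP the outcome is "Primary Outcome: ED visit [Time Frame: within 120 days following day of discharge", and the question put to it is "Question: Does outreach decrease ED visits when including information about follow-up care".

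Under Other Pre-specified Outcomes the SAP says "We will run the analysis described above on the following additional outcomes". It lists eight, all of them appointments scheduled or attended, at 7, 14, 30 and 60 days. The word unnecessary is not defined, and no listed outcome uses return-visit acuity, disposition, admission or death.

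**The concern.** A reader who takes the first sentence of the Background as the trial's objective sees a mismatch. The goal names unnecessary visits; the outcome counts all visits. The patients are high-acuity by title, so some of their returns to the ED may well be needed. A message that steers them towards other care could remove avoidable visits, prevent deterioration or deter visits that should have happened. A fall from 33% to 30% would look the same in each case.

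If the trial went on to report fewer unnecessary visits from that result, the conclusion would not be supported by its data. That is what would be at stake.

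**Working it through.** **Step 1: what the trial commits itself to.** Set the statements side by side.

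| Place | What it concerns |
|---|---|
| Background, first sentence | Campaign goal: unnecessary ED visits / follow-up |
| Background, study aim | ED use, unqualified |
| Objectives, last sentence | ED use, unqualified |
| Power Analysis | Subsequent ED visits, unqualified |
| SAP, question and hypothesis | ED visits, unqualified |
| SAP, primary outcome | ED visit within 120 days, unqualified |
| SAP, other outcomes 1–8 | Appointments scheduled or attended |

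The qualifier occurs once, in a sentence whose subject is the campaign and which joins two goals with a slash. Every statement about what the study assesses, tests or is sized for omits it. Aim, hypothesis, outcome and sample size therefore agree with one another, and the follow-up goal has its own outcomes.

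**Step 2: the plan's own figure.** Inputs from the Power Analysis: 7,500 patients, 33% control rate, 3.0-point decrease, two-sided alpha .15. Assumption: equal arms, 7,500 / 3 = 2,500, since the allocation ratio is not stated.

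- Standard error under no difference: √(2 × 0.315 × 0.685 / 2,500) = 0.01314
- Standard error under the alternative: √((0.33 × 0.67 + 0.30 × 0.70) / 2,500) = 0.01313
- Power: Φ((0.03 − 1.4395 × 0.01314) / 0.01313) = Φ(0.844) = 0.801

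The stated 80% reproduces for the any-visit outcome. The trial is sized for the quantity it says it will study.

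**Step 3: what the outcome leaves open.** The documents do not say what share of visits is unnecessary. Assume 20% to 80% of the 33%, that is 6.6% to 26.4% of patients. A 3-point fall confined to those visits would be a relative cut of 3 / 6.6 = 45% down to 3 / 26.4 = 11%. A uniform cut of 3 / 33 = 9.1% would take only 0.6 to 2.4 points from them. The primary result is 33% against 30% throughout. This is a true limit on interpretation, but it lies outside the stated study aim.

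**Step 4: would a split of return visits remove that limit?** Assume 10% to 20% of control patients have only low-acuity returns (pL) and the remaining 23% to 13% have a serious one (pS). The per-patient variance of the contrast between the two is pL + pS − (pL − pS)². Suppose the whole 3-point fall is in the low-acuity part.

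- 10% falling to 7%, with 23% unchanged: variances 0.3131 and 0.2744; SE = √(0.5875 / 2,500) = 1.53 points; 95% half-width 1.96 × 1.53 = 3.0 points; power 70% at alpha .15 and 50% at .05.
- 20% falling to 17%, with 13% unchanged: variances 0.3251 and 0.2984; SE = √(0.6235 / 2,500) = 1.58 points; half-width 3.1 points; power 68% and 48%.

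Putting the whole fall in the serious part gives results between these two. If the fall is instead proportional, power within a component is 37% to 64% at .15. For death, at assumed rates of 1% and 2%, the half-width 1.96 × √(2p(1 − p) / 2,500) is 0.55 and 0.78 points, or 55% and 39% of the rate itself.

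The split is also not a measure of necessity. Among patients with a high-acuity index visit, an avoidable return may itself be high-acuity, and a fall in serious visits could mean prevented illness or deterred care.

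**The case for a change.** The strongest counter-argument is that the follow-up half of the goal has eight outcomes while the half about unnecessary visits has none that can identify it, and that the outreach itself addresses non-emergent situations. The Power Analysis treats an effect of the target size as useful; whether it is useful for the campaign depends on which visits fell. A descriptive breakdown would leave the primary outcome, model and sample size alone. It would also show a concentrated shift quite well: under the assumed rates, a 3-point fall wholly within one component would be detected with 87% to 99% power at alpha .15. The Project Status section says no messages had been sent, so it could still have been pre-specified.

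The factual part of this stands: no outcome describes the ED visits themselves, and such a breakdown would be informative reading. It does not show a fault. The favourable power figures need the entire effect to fall in one component, and every component rate is assumed. The documents do not describe the data extract, so the claim that the extra fields are cheap to obtain is also an assumption. The one element that costs nothing, keeping conclusions at ED use, is how the study aim is already worded.

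**Conclusion.** The concern does not hold. Followed as written, the plan gives a valid randomised comparison of any ED visit within 120 days and supports a sound conclusion about ED use, which is what it says it will assess. Nothing in the documents commits the trial to claiming a fall in unnecessary visits. The effect on the primary test, model and sample size is nil: the stated power reproduces at 80.1% against 80%, assuming equal arms. What remains is a preference for additional descriptive outcomes. These would not establish necessity and, under the assumed component rates, would leave the contrast between visit types uncertain by about ±3 points. The verdict rests on reading the opening sentence of the Background as a statement about the campaign, which its own wording and the separate study aim in the same paragraph support. A report that claimed fewer unnecessary visits would go beyond the plan; the plan itself does not.

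### Optional improvement, not an error: the primary OLS model names arm as its only predictor; pre-specifying prior ED visits, age and sex could modestly improve precision at low cost

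*Combined protocol and SAP*

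**What the plan says.** Under Planned Analyses, Primary Outcome, the SAP states: "We will run an OLS regression including a categorical predictor variable coding for experimental arm", with levels "0 = control arm, 1 = single message arm, 2 = message plus reminder arm". The word *including* does not strictly rule out other predictors, but none is pre-specified in that section, under Other Pre-specified Outcomes or in the Analysis Notes. The type of standard error is not stated either.

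The same model carries over to eight scheduling and attendance outcomes: "We will run the analysis described above on the following additional outcomes".

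The Power Analysis says that with 7,500 patients "we would have 80% power to detect a 3.0% absolute decrease in ED visits between each active arm and the control arm", at two-tailed alpha .15 and a 33% control rate. It adds that "The target effect size and number of patients are largely informed by practical considerations" and that the intervention runs for a "maximum of 6 months, regardless of whether the full sample is achieved". Project Status records that at upload "no messages have been sent or data collected or analyzed".

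**The concern.** Nothing in the planned analysis is invalid. The question is whether it gives up precision that could be had almost for free. The primary outcome requires ED visits to be captured in records, so visits before the index discharge may be obtainable from the same source. A patient's earlier ED use is a natural candidate for predicting later use. In a linear model, adding such a covariate leaves the arm coefficient as a risk difference and can reduce its standard error.

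The gain could be useful here because the design has almost no slack. About 7,478 patients are needed for 80% power and 7,500 are planned, while enrolment may end at six months whatever the count. The plan openly accepts that trade-off. Covariates cannot add patients, but they might recover part of any lost power.

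**Working it through.** **Inputs from the Power Analysis:** control rate .33; active-arm rate .33 − .03 = .30; two-sided alpha .15; 7,500 patients. Three arms are stated under Design. **Assumptions:** equal allocation (2,500 per arm), because no ratio is stated, and every R-squared value below.

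**Step 1: the plan's own figure.**

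- SE = √[(.33×.67 + .30×.70)/2,500] = √(.4311/2,500) = .01313
- z(.925) = 1.4395
- Power = Φ(.03/.01313 − 1.4395) = 80.1%
- Total N for 80% power = 3 × (1.4395 + .8416)² × .4311/.03² = 7,478

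The stated 80% reproduces without covariates. A pooled-variance formula gives 7,485 and the same 80.1%.

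**Step 2: effect of adjustment.** Residual variance is multiplied by (1 − R²), so:

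- power = Φ(.03/[SE√(1 − R²)] − 1.4395)
- 85% CI half-width = 1.4395 × SE × √(1 − R²)
- equivalent extra patients = 7,500 × R²/(1 − R²)

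| Assumed R² | Power, 7,500 | Half-width, 7,500 (points) | Equivalent extra patients | Power, 7,000 |
|---|---|---|---|---|
| 0 | 80.1% | 1.89 | 0 | 77.9% |
| .02 | 80.7% | 1.87 | 153 | 78.5% |
| .05 | 81.7% | 1.84 | 395 | 79.5% |
| .10 | 83.4% | 1.79 | 833 | 81.2% |
| .15 | 85.0% | 1.74 | 1,324 | 83.0% |

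**Step 3: R² needed to regain 80% after a shortfall.** This is 1 − N/7,478: .030 at 7,250 patients, .064 at 7,000 and .131 at 6,500.

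**Step 4: what such an R² means.** Suppose 40% of patients had an ED visit in the prior year, with revisit risk 45% against 25% in the rest (all assumed). The overall rate is .4×.45 + .6×.25 = .33, as in the plan.

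- R² = q(1 − q)(r₁ − r₀)²/[m(1 − m)] = .24 × .04/(.33×.67) = .043
- Power is 81.5% at 7,500 patients and 79.3% at 7,000.
- To reach .064, the risk gap must be √(.064 × .33 × .67/.24) = .243, or about 47.6% against 23.3%.

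**Step 5: simulation** (40,000 trials, additive OLS with HC2 standard errors, Monte Carlo error about 0.2 points).

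| Scenario | Unadjusted | Adjusted |
|---|---|---|
| R² .043, 2,500 per arm | 79.8% | 81.4% |
| R² .043, 2,333 per arm | 78.2% | 79.5% |
| R² .064, 2,333 per arm | 77.6% | 79.8% |
| Useless covariate | 79.9% | 80.0% |
| No treatment effect (nominal 15%) | 15.2% | 15.1% |

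Mean estimates lay between −.0299 and −.0301, so adjustment introduced no bias. A useless covariate cost nothing measurable.

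**Step 6: standard-error type.** The default OLS standard error for a pair of arms is √(2 × mean of p(1 − p) over the three arms/2,500).

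- Primary outcome (.33/.30/.30): .01308 against a true .01313 for active versus control, a ratio of 0.996.
- Assumed scheduling rates of 10/25/30% or 20/25/28% (control/single/reminder): the ratio is 1.01 to 1.08 for active versus control, slightly conservative. It is 0.90 to 0.97 for reminder versus single.

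**The case against.** The strongest reply is that no defect exists. An arm-only linear model in a randomized trial of 7,500 is legitimate and transparent, it matches its power calculation, and the SAP gives a reason for using OLS. That stands, and is why this is only an optional improvement.

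Further points limit the size of the benefit:

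- R-squared is unknown. The 5-point gain needs .15, whereas the worked example gives 1.4 points (81.5% − 80.1%).
- The plan accepts the possibility of a shortfall but forecasts none.
- The worked example and simulation use a single covariate. The proposed set (a visit count, age and sex) was not itself modelled.
- No gain is claimed for the eight other outcomes. Extending the covariates to them serves consistency, because the SAP reuses one model throughout.
- The documents list no baseline fields. The chart is mentioned only as the source of the randomization number, so low cost is plausible but not shown.
- Robust standard errors matter little. Default errors would be too small only for reminder versus single, and no section names that test. The Objectives do seek the most effective version, and the Background asks "whether patients followed through on the message-specific calls to action in the messages differently across conditions", so the comparison could still be made.

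None of this shows that adjustment would bias or weaken the result.

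**Conclusion.** The point holds as a low-priority, optional improvement. The planned analysis is unbiased and adequate for its stated 80% power. Adjustment would raise power by 0.6 to about 5 points for assumed R-squared values of .02 to .15, with a gain of one to two points at the middling values of .043 to .05. It would partly offset a shortfall, and fully offset 500 missing patients only at an R-squared of about .064 or more. These figures rest on equal allocation, on R-squared values that the documents do not supply, on the baseline fields being extractable, and on one index visit per patient, which is not stated. Confidence in the size of the gain is therefore moderate at best. The near-absence of a power penalty is better supported.

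**What to change.** First confirm that the three fields can be extracted for all randomized patients and that each patient contributes one index visit. Then add to the SAP:

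> The primary and other OLS models will include arm plus three covariates fixed before index discharge: number of ED visits in the 12 months before the index visit, age and sex. Robust (HC2 or HC3) standard errors will be used. The arm-only model will be reported as a sensitivity analysis.

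Fix this text before outcome data are analysed. Since no data had been collected at upload, it could have been pre-specified cleanly from that point. If the team prefers the arm-only model, a sentence saying that no covariates will be used would remove the open analyst choice.

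The cost is one extra chart-data pull, a few lines of text and slightly more analysis work. No patients or procedures are added, and the estimand remains the risk difference.

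### For the two 7-day outcomes the active arms are, as described, the same treatment, but the SAP specifies no combined-active versus control estimate

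*Combined protocol and SAP*

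**What the plan says.** The Methods section gives the single-notice arm its follow-up suggestions "via SMS messages at 1 day post discharge and in their AVS" and the reminder arm the same suggestions "via SMS messages at 1 and 8 days post discharge and in their AVS". The sentences on the scheduling phone number and the self-scheduling link match. The day-8 text is the only stated difference.

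Under Other Pre-specified Outcomes, items 1 (scheduled) and 2 (attended) carry the window "Time Frame: within 7 days following day of discharge". The instruction for all eight items is "We will run the analysis described above on the following additional outcomes". That analysis, under Planned Analyses, is an OLS regression with a "categorical predictor variable coding for experimental arm (0 = control arm, 1 = single message arm, 2 = message plus reminder arm"). No contrast between arms is written out for any outcome.

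Two other statements bear on whether pooling was intended. The primary hypothesis is that "SMS text plus AVS outreach (with or without reminder) decreases the likelihood patients will visit the ED", which leans towards one overall outreach question. The Power Analysis compares rates "between each active arm and the control arm, with two-tailed alpha of .15", which keeps the arms apart.

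**The concern.** A 7-day window closes before a day-8 text is sent. For items 1 and 2, then, the two active arms are two randomized groups given one described treatment, and everyone in both can inform the estimate of its effect against control. The carried-over model instead gives two separate coefficients, each ignoring half of the treated patients if the arms are equal.

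Nothing is biased; what is lost is precision on the plan's earliest reading of the response to the day-1 text and the AVS. There is also some risk of misreading. If one arm's 7-day coefficient is significant and the other's is not, a reader may credit or blame a reminder that had not yet gone out. A combined estimate could be computed later from the arm counts, but it would not then be pre-specified.

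**Working it through.** **Inputs.** From the Power Analysis: 7,500 patients, 80% power, 33% versus 30%, two-tailed alpha .15. The allocation ratio is not given: assignment is "based on which of several ranges of randomized numbers that patient was originally assigned in their electronic chart", and the sizes of the ranges are not stated. No control rates are given for the 7-day outcomes, and alpha is stated only for the ED power calculation. I therefore assume three splits (control : single notice : reminder), control rates of 10%, 30% and 50%, and alpha .15 throughout (z = 1.4395; z for 80% power = 0.8416; sum 2.2811).

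**Step 1: reproduce the plan's figure.** Power = Φ(0.03/SE − 1.4395), with SE = √(0.33·0.67/n₀ + 0.30·0.70/n₁).

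- 1:1:1 (2,500 v 2,500): SE = 0.01313; Φ(2.285 − 1.440) = 80.1%.
- 2:1:1 (3,750 v 1,875): SE = 0.01308; Φ(2.294 − 1.440) = 80.4%.
- 1:2:2 (1,500 v 3,000): SE = 0.01474; Φ(2.035 − 1.440) = 72.4%.

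The stated 80% fits the first two splits and not the third.

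**Step 2: precision gained by combining.** SE ratio = √[(1/n₀ + 1/(n₁+n₂)) / (1/n₀ + 1/n₁)].

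- 1:1:1: √[(1/2500 + 1/5000)/(2/2500)] = √0.75 = 0.866, a 13.4% smaller SE.
- 2:1:1: √[(1/3750 + 1/3750)/(1/3750 + 1/1875)] = √(2/3) = 0.816, 18.4% smaller.
- 1:2:2: √[(1/1500 + 1/6000)/(1/1500 + 1/3000)] = √(5/6) = 0.913, 8.7% smaller.

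The direction does not depend on the split, because 1/(n₁+n₂) is always below 1/n₁.

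**Step 3: power.** Take an effect with 80% power per arm, so effect/SE = 2.2811. Dividing by the SE ratio and subtracting 1.4395 gives the combined power (the opposite tail is negligible).

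- 1:1:1: Φ(2.634 − 1.440) = 88.4%.
- 2:1:1: Φ(2.794 − 1.440) = 91.2%.
- 1:2:2: Φ(2.499 − 1.440) = 85.5%.

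**Step 4: detectable difference at 80% power, 1:1:1.** 2.2811·√[p(1−p)(1/2500 + 1/n_active)], with n_active = 2,500 per arm or 5,000 combined.

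| Control rate | Per arm | Combined |
|---|---|---|
| 10% | 1.94 points | 1.68 points |
| 30% | 2.96 | 2.56 |
| 50% | 3.23 | 2.79 |

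The gain is roughly 0.3 to 0.4 points.

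**Step 5: discordant per-arm results.** With 1:1:1 the two test statistics share a control group and correlate at 0.5. If each has 80% power, the chance that both are significant in the expected direction is about 68.7%. The chance that exactly one is significant is 2 × (80% − 68.7%), or about 23%, although both arms had the same described treatment.

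**Step 6: how to combine.** A single active-versus-control indicator gives the same point estimate as the average of the two arm coefficients weighted by arm size. A simple average matches it only when the active arms are equal. With 2,500 controls, the simple average's SE is 1.007 times that of the single indicator at 2,000/3,000, 1.031 times at 1,500/3,500 and 1.090 times at 1,000/4,000.

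**The case against.** The strongest reply is that this is a preference and not a fault. Nothing in the plan contradicts itself here, the per-arm estimates are valid, and the combined estimate can be recovered from arm counts. The Background section says the study will examine whether follow-through on the calls to action differs across conditions, which is a reason to keep the arms separate. The hypothesis wording may already intend pooling. The message and AVS texts are not shown, so identical content up to day 7 is inferred. The practical size depends on an assumed allocation, assumed rates and a borrowed alpha. An extra estimate also adds to a plan with no stated multiplicity handling, and the headline quantity would differ between 7 days and the later windows.

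Much of this stands as a limit on importance. It does not remove the point. The hypothesis phrase concerns ED visits and names no estimator, while the arm coding and the power statement keep the arms apart; if pooling was meant, it still needs writing down. The across-conditions aim is still served if per-arm coefficients are reported, and these also keep the windows comparable. The assumptions change the size of the gain but not its direction. On multiplicity, naming one estimate of interest per 7-day outcome at least makes clear which result leads. The broader gap, that no contrast is named for any outcome, is a separate matter.

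**Conclusion.** The point holds, as a minor improvement and not an error. For items 1 and 2 the active arms are one treatment as described, and the planned per-arm comparisons leave precision unused: 13.4% of the standard error under equal allocation, and 8.7% to 18.4% across the splits tried. The plan's own power figure fits the 13% to 18% end better.

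This rests on three assumptions: that outreach content is the same in both active arms until day 8; that 7,500 patients are enrolled in one of the assumed splits; and, for the power and detectable-difference figures, alpha .15 and control rates of 10% to 50%. Two of eight additional outcomes are affected, and no decision rule in the document rests on them. The 120-day ED outcome, the sample size and the 14-, 30- and 60-day outcomes are untouched.

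**What to change.** Keep the three-level arm model for every outcome and add one sentence to the SAP along these lines:

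*For the two 7-day outcomes the estimate of interest is both active arms combined versus control, from a single active-arm indicator (equivalently, the two arm coefficients averaged with weights proportional to arm size). Per-arm coefficients are also reported, and any 7-day difference between the active arms is read as a check on randomization and delivery, because the reminder has not yet been sent.*

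Do not use an unweighted average unless the active arms are equal in size. If the AVS or day-1 text does differ between the active arms, say so and leave the per-arm analysis as it is.

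The cost is that sentence and one extra estimate per 7-day outcome, with no new data. The Project Status section reports that no messages had been sent and no data collected at the document date, so the contrast could be fully pre-specified at that point.
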